8.1.11. Protocol Deviations Because of an Adverse Event

If a patient experiences an adverse event or medical emergency, deviations from the protocol may be allowed on a case-by-case basis. To ensure patient safety, after the event has stabilized or treatment has been administered (or both), the investigator or other physician in attendance must

contact the physician identified in the Clinical Study Personnel Contact Information section of this protocol as soon as possible to discuss the situation. The investigator, in consultation with the sponsor, will decide whether the patient should continue to participate in the study.

8.2. Assessment of Local Tolerability and Pain

Local tolerability assessments should be performed at each administration of IMP ([Table 1](#)) and include administration site findings and pain. Administration site findings (erythema, ecchymosis, induration, tenderness, warmth, and swelling) will be assessed using the scales provided in [Table 6](#). Pain at the administration site will be reported using a standardized 11-point numeric rating scale (NRS-11) for pain intensity, where 0 is “No pain” and 10 is “Worst possible pain.” Patients will be asked to respond to the following question: “How much pain do you feel at the drug injection site?”

Pain will be assessed beginning, during (approximately midway through the infusion), and after the completion of IMP administration and 1 hour later. Administration site findings will be assessed after the completion of IMP administration and 1 hour later. Additionally, after the loading dose and first induction dose, assessments will also be performed 2 hours after the completion of IMP administration. Allowed time windows for the local tolerability assessments after the completion of the infusion are ± 15 minutes.

Severity of local tolerability symptoms should be assessed as described in [Table 6](#). The surface diameter in millimeters should be recorded, and erythema, induration, and ecchymosis at the administration site will be graded according to the diameter measurements: absent, 5 mm to ≤ 50 mm (mild), >50 to ≤ 100 mm (moderate), and >100 mm (severe). Erythema, ecchymosis, and induration under 5 mm in diameter should be assessed as absent. Care should be taken to avoid pressuring or squeezing the administration site while assessing induration via careful superficial palpation.

In the case that findings do not resolve while the patient remains at the study center, additional evaluation should take place thereafter at each visit until resolution occurs. Administration sites may be photographed, including between visits to the study center, to provide visual representation in addition to comments in the source documents. Any features that could be used to identify the patient will not be captured on the photograph. Appropriate treatment for administration site finding or pain may be provided if necessary, in which case such treatments must be recorded as concomitant medication(s).

Table 6: Administration Site Finding Severity Assessment

Test	Response
Erythema	
 - Absent - Erythema surface diameter 5 to \leq50 mm (mild) - Erythema surface diameter >50 to \leq100 mm (moderate) - Erythema surface diameter >100 mm (severe)
Ecchymosis	
 - Absent - Ecchymosis surface diameter 5 to \leq50 mm (mild) - Ecchymosis surface diameter >50 to \leq100 mm (moderate) - Ecchymosis surface diameter >100 mm (severe)
Induration	
 - Absent - Induration surface diameter 5 to \leq50 mm (mild) - Induration surface diameter >50 to \leq100 mm (moderate) - Induration surface diameter >100 mm (severe)
Tenderness	
 - None
Warmth	
 - Mild
Swelling	
 - Moderate - Severe

Administration site findings described in [Table 6](#) and administration site pain will be recorded on specified CRF and will not require additional recording in the adverse events form. Administration site findings with characteristics that are not described in [Table 6](#) (eg, lipoatrophy, necrosis, abscess) or fulfill seriousness criteria must be recorded and reported as adverse events or serious adverse events as specified in [Section 8.1.3](#) and [Section 8.1.8](#).

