2.2.2.1.2. Safety

No deaths, serious adverse events, protocol-defined adverse events of special interest (PDAESIs; severe hypersensitivity reactions or anaphylaxis), or withdrawals due to adverse events were reported during the study.

No adverse events consistent with immunosuppression (including opportunistic or unusual infections), cytopenias, or systemic reactions were reported, and no safety signal with

treatment-emergent ADA responses was observed. The nature and incidence of the adverse events were similar between doses and comparable with those for placebo. There were no dose-related trends and no clinically meaningful differences observed between the treatment groups for laboratory tests, vital signs, electrocardiograms (ECGs), and physical examination findings.

The safety data of Study TV48574-SAD-10126 do not suggest any adverse drug reactions associated with TEV-48574 treatment except for transient nonserious injection site findings.

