
A secondary objective of the study is to evaluate the safety and tolerability of 2 different doses of TEV-48574 sc administered Q2W in adult patients with IBD (moderate to severe UC or CD).
	
The safety and tolerability measures/parameters are as follows:
 
 • Adverse events • Change from baseline in clinical laboratory test results (serum chemistry, hematology, and urinalysis) • Change from baseline in vital signs measurements (blood pressure, pulse rate, body temperature, and respiratory rate) • Change from baseline in 12-lead electrocardiogram findings • Patients who stopped the investigational medicinal product due to adverse events • Local tolerability at the injection site

A secondary objective of the study is to evaluate the immunogenicity of 2 different doses of TEV-48574 sc administered Q2W in adult patients with IBD (moderate to severe UC or CD).
	
The immunogenicity endpoints for this study are as follows:
 
 • Change from baseline in treatment-emergent anti-drug antibody (ADA) at weeks 2, 4, 8, 14, and follow-up visit • Presence of neutralizing ADA in ADA positive patients at weeks 2, 4, 8, 14, and follow-up visit

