If any of the following criteria occur, study drug should be withheld and additional monitoring and follow-up assessment will be required (as detailed in the Liver Safety Required Actions and Follow-up Assessments section in [Appendix K](#)):

- ALT or AST ≥ 5 x ULN
- ALT or AST ≥ 3 x ULN with the appearance of fatigue, nausea, vomiting, right upper quadrant pain or tenderness, fever, rash, and/or eosinophilia ($>5\%$)
- AST and/or ALT ≥ 3 fold ULN combined with an elevation of total bilirubin ≥ 2 fold ULN measured in the same blood draw sample or in combination with clinical jaundice or INR >1.5 (not applicable for patients on anticoagulants)

The additional information will be recorded on the Liver Event CRF.

The most appropriate diagnosis or the abnormal laboratory values (if a diagnosis cannot be established) should be recorded on the Adverse Event eCRF (see Section [8.1.3](#)) and reported to the Sponsor immediately (ie, no more than 24 hours after learning of the event).

Severe hematology abnormalities

Predefined confirmed hematology stopping criteria (see Section [4.4.1](#)) should be re-tested every 3 to 5 days until values have returned to above the hematological exclusion criteria threshold, at which point dosing can be resumed (however, two consecutive doses of IMP, should never be given less than 7 days apart).

8.1.10.2. Protocol-Defined Adverse Events of Special Interest that Do Not Require Reporting to Sponsor's Global Patient Safety and Pharmacovigilance

The following are considered protocol-defined adverse events of special interest that do not need to be sent to the sponsor's GPSP department (unless assessed as serious) and will be recorded only in the clinical database:

- administration site reactions (as described in Section [8.2](#))

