10.8. Tolerability Analysis

Tolerability will be assessed by the number (%) of patients who fail to complete the study due to adverse events.

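### Section 8.2 does not require an adverse event entry for a non-serious site reaction even when it ends treatment, so the AE-based stopping and tolerability counts may miss it

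*Protocol*

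**What the plan says.** **Recording.** Protocol Section 8.2 sends the Table 6 findings (erythema, ecchymosis, induration, tenderness, warmth, swelling) and site pain to a dedicated page: these findings and "administration site pain will be recorded on specified CRF and will not require additional recording in the adverse events form". There are two exceptions: findings with features that Table 6 does not describe, and those that "or fulfill seriousness criteria must be recorded and reported as adverse events or serious adverse events as specified in" the general reporting sections. Grade and effect on treatment are not exceptions.

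**Classification.** Section 8.1.10.2 opens with "The following are considered protocol-defined adverse events of special interest that do not need to be sent" to the sponsor's safety department. Its only entry is administration site reactions, with a reference to Section 8.2. Both sections therefore concern the same events.

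**Outputs.** The secondary safety endpoints in Section 3.1 include "Patients who stopped the investigational medicinal product due to adverse events" and, separately, local tolerability at the injection site. Section 10.7 summarises and lists coded adverse events that cause withdrawal, and also tabulates local tolerability scores by time point. Section 10.8 is one sentence: "Tolerability will be assessed by the number (%) of patients who fail to complete the study due to adverse events".

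**Timing.** Under Section 8.2, "Administration site findings will be assessed after the completion of IMP administration and 1 hour later", with a further look at 2 hours after the loading dose and the first induction dose. Findings still present when the patient leaves are checked again at each visit until they resolve.

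**The concern.** The safety summary of the first-in-human study (Section 2.2.2.1.2) suggests no adverse drug reactions "except for transient nonserious injection site findings". Site reactions are thus the one reaction that earlier study points to, and this trial gives 15 mL at a single site followed by 6 mL doses (12 mL for patients randomized before Amendment 03 with Revision 01). If a patient finds the infusions intolerable because of the site, that is a tolerability failure in the plain sense. Yet the rule on what sites must enter does not guarantee the record on which the tolerability outputs depend.

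This is a data collection rule. If sites follow it as written and enter no adverse event, no later analysis plan can recover the coded term, the relationship to the product or the action taken with the product.

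**Working it through.** The plan gives no figure on this point, so the check sets the rules side by side and follows one patient through them.

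**1. A patient stops the product because of a large, non-serious induration.**
- Local tolerability page (8.2): diameter and grade recorded.
- AE form: Section 8.1.3 would require an entry with action taken, relationship and severity, but Section 8.2 waives it. Entry is optional.
- Discontinuation page (5.3): primary reason recorded. Because 8.1.10.2 calls the reaction an adverse event, the site may give an adverse event as the reason. Nothing in 8.2 tells it to.

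**2. Where that patient appears if the site uses the waiver.**

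| Output | Source it needs | Patient present? |
|---|---|---|
| Reasons for stopping (10.4.1) | Discontinuation page | Yes, under whatever reason was given |
| Local tolerability scores (10.7) | Local tolerability page | Yes, but not linked to stopping |
| Product stopped due to AEs (3.1) | Not stated | Only if taken from the discontinuation page with an adverse event as the reason |
| Coded AEs causing withdrawal (10.7), if the patient also leaves the study | AE form | No |
| Non-completion due to AEs (10.8), if the patient also leaves the study | Not stated | As for the 3.1 endpoint |

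The coded withdrawal table and the disposition table can therefore disagree about the same patient, with both produced according to the protocol.

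**3. Size per missed patient.** Table 2 plans 40 UC and 40 CD patients per arm.
- Pooled: 1/(40 + 40) = 1/80 = 1.25 percentage points.
- One indication: 1/40 = 2.5 percentage points.

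The number of such patients is not in the protocol. Assuming 0 to 3 in an arm, the pooled rate would be understated by 0, 1.25, 2.5 or 3.75 points. If all fell in one indication, the understatement there would be 0, 2.5, 5.0 or 7.5 points.

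**4. Late onset.** Scheduled site looks: 7 infusions × 2 (completion and 1 hour) + 2 extra looks at 2 hours = 16. Doses are 14 days apart. Table 1 schedules local tolerability at visits 1 to 7 only, so after the seventh dose (day 85) none is planned at day 99 or day 127. The repeat-evaluation rule applies to findings that had not cleared before the patient left. A reaction that starts at home is outside it. If the reaction is of a Table 6 type, it also falls under the AE-form waiver. No form is named for it.

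**The case against.** The strongest reply is that these reactions are well covered already, and most of it stands.

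- Local tolerability is a secondary endpoint of its own, solicited, graded and tabulated. Site reactions do not disappear from the safety objective.
- Section 8.2 says that an AE entry is not required; it does not forbid one. Serious and atypical findings must be reported.
- Section 5.3 puts the primary reason for every stop on the CRF and Section 10.4.1 summarises it. A count taken from that page could include these patients, and the choice of source may be settled in an analysis plan that is not shown.
- Section 8.1.3 requires an open question about adverse events at each contact, so late reactions can be elicited. The local tolerability page carries no stated time limit. A reader might infer that late reactions are recorded nowhere; the documents do not support that.
- Neither earlier study reports a withdrawal or early termination due to an adverse event (Sections 2.2.2.1.2 and 2.2.2.3), so such stops may be rare.

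Three further inferences are tempting and also fail. First, that severe site reactions are lost from the grade 3/4 safety monitoring: Table 6 grades erythema, ecchymosis and induration by diameter, adverse events are graded by CTCAE or Table 4, and nothing shows that a diameter above 100 mm is grade 3. Second, that the omission favours active drug: placebo has the same formulation without protein, the same volume and the same rate, and no rates by arm are given. Third, that the short observation time, or the serum peak at 72 to 96 hours, measures what is missed: scheduled looks are not the only route of capture, and no passage links serum concentration to the onset of local reactions.

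The gap for a non-serious reaction that ends treatment remains. The coded withdrawal summary in Section 10.7 needs an AE entry, and Section 8.2 waives it.

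**Conclusion.** The point holds in a narrow form. A non-serious Table 6 finding or site pain that leads to interruption, discontinuation or withdrawal need not be entered as an adverse event, although another section calls it one. Such patients may be missed in the AE-discontinuation endpoint, the coded withdrawal summaries and the tolerability analysis. It cannot be said that they are missing, since that depends on what sites enter and on the data source used. Late reactions lack a scheduled assessment and a named form, but not every route of capture.

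The size is 1.25 points per missed patient in a pooled arm of 80, or 2.5 points in an arm of 40. This assumes the planned arm sizes and says nothing about how often it happens. No efficacy conclusion is affected. It is a cheap improvement, worth making because the entries cannot be recreated afterwards by analysis.

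**What to change.** These changes concern recording only and alter no treatment rule.

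- Keep the local tolerability page as it is.
- In Section 8.2, add that a Table 6 finding or site pain that leads to interruption or discontinuation of the product, or to study withdrawal, is also entered on the AE form as an adverse event of special interest.
- In Section 8.2, add that a reaction reported after the last scheduled assessment of a visit is recorded with onset date and grade, and name the form: either the AE form or the local tolerability page.
- In Section 10.8, state that discontinuations for site reactions count as discontinuations due to adverse events.

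The cost is a few sentences and a CRF completion note. The downside is a few more AE entries and a slightly higher reported AE rate.

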8.3. Pregnancy

Any female patient becoming pregnant during the screening period will be considered a screen failure and will not be allowed to rescreen.

Any female patient becoming pregnant during the study will discontinue IMP.

All pregnancies of women participating in the study and female partners of men participating in the study, if applicable, that occur during the study, or within 5 half-lives (50 days) of the last IMP administration, are to be reported immediately to the individual identified in the Clinical Study Personnel Contact Information section of this protocol, and the investigator must provide the sponsor (LSO/CRO) with the completed pregnancy form. The process for reporting a pregnancy is the same as that for reporting a serious adverse event but using the pregnancy form ([Section 8.1.8](#)).

All female patients and female partners of men participating in the study (female partners of men participating in the study who become pregnant will be asked to sign an ICF) who become pregnant will be monitored for the outcome of the pregnancy (including spontaneous, elective, or voluntary abortion). If the pregnancy continues to term, the outcome (health of the infant up to 8 weeks of age), including details of birth and presence or absence of any birth defect, congenital abnormalities, or maternal and newborn complications, will be reported to the sponsor. Any

complication of pregnancy during the study and any complication of pregnancy that the investigator becomes aware of after withdrawal from the study will be reported as an adverse event or serious adverse event, as appropriate.

If the pregnancy in the woman participating in the study and/or the female partners of men participating in the study does not continue to term, 1 of the following actions will be taken:

- For a spontaneous abortion, report as a serious adverse event (in addition to the pregnancy form).
- For an elective abortion due to developmental anomalies, report as a serious adverse event (in addition to the pregnancy form).
- For an elective abortion **not** due to developmental anomalies, report on the pregnancy form; do not report as an adverse event.

8.4. Medication Error and Special Situations Related to the Investigational Medicinal Products

Any administration of IMP that is not in accordance with the study protocol should be reported in the patients' source documents, regardless of whether or not an adverse event occurs as a result. When meeting important protocol deviation criteria ([Appendix B](#)), all instances of incorrect IMP administration should be categorized as "Noncompliance to Investigational Medicinal Product (IMP)."

The following are types of medication errors and special situations:

1. Medication error: Any unintentional error in the prescribing, dispensing, or administration of a medicinal product while in the control of the healthcare professional, patient, or consumer.
2. Overdose: Administration of a quantity of a medicinal product given per administration or cumulatively, which is above the maximum recommended dose according to the authorized product information/study protocol. Clinical judgment should always be applied. Any dose of IMP (whether the test IMP or placebo IMP), whether taken intentionally or unintentionally, in excess of that prescribed must be immediately reported to the sponsor.
3. Misuse: Situations where the IMP is intentionally and inappropriately used not in accordance with the authorized product information/study protocol.
4. Abuse: Persistent or sporadic, intentional excessive use of IMP, which is accompanied by harmful physical or psychological effects.
5. Off-label use: Situations where an IMP is intentionally used for a medical purpose not in accordance with the authorized product information/study protocol.
6. Occupational exposure: Exposure to an IMP, as a result of one's professional or non-professional occupation.
7. Breastfeeding: Suspected adverse reactions, which occur in infants following exposure to a medicinal product from breast milk.

8.5. Clinical Laboratory Tests

All clinical laboratory test results outside of the reference range will be judged by the investigator as belonging to 1 of the following categories:

- abnormal and not clinically significant
- abnormal and clinically significant

A laboratory test result that is judged by the investigator as clinically significant will be recorded both on the source documentation and the CRF as an adverse event and monitored as described in Section 8.1.3. A laboratory or diagnostic test abnormality (once confirmed by repeated testing) that results in the withdrawal of the patient from the study; the temporary or permanent withdrawal of IMP or medical treatment, or further diagnostic work-up may be considered adverse events. If further diagnostic work-up of abnormal laboratory result leads to the investigator concluding that the initial abnormality was not clinically significant, it is at the investigator's discretion whether or not the laboratory result triggering the work-up is an adverse event. (Note: Abnormal laboratory or diagnostic test results at the screening visit(s) that preclude a patient from entering the study or receiving IMP are not considered adverse events.)

Table 7: Clinical Laboratory Tests

Serum Chemistry	Hematology and Coagulation ^a	Urinalysis
Calcium	Hemoglobin	Protein
Phosphate	Hematocrit	Glucose
Sodium	Erythrocytes	Ketones
Potassium	Platelets	Hemoglobin
Chloride	Leucocytes	pH
Creatinine	
 • Neutrophils 	Specific gravity
Glucose	
 • Lymphocytes 	Microscopic tests
Blood urea nitrogen (BUN)	
 • Eosinophils 	
 • Bacteria
Low density lipoprotein (LDL) ^b	
 • Monocytes 	
 • Erythrocytes
High density lipoprotein (HDL) ^b	
 • Basophils 	
 • Leucocytes
Triglycerides ^b	Prothrombin International Normalized Ratio (INR)	
 • Crystals
Urate	Prothrombin time (PT)	
 • Casts
Alanine aminotransferase (ALT)	Partial thromboplastin time (PTT)	
Aspartate aminotransferase (AST)		
Lactate dehydrogenase (LDH)		
Gamma-glutamyl transpeptidase (GGT)		
Alkaline phosphatase		
Bicarbonate		
Protein		
Albumin		
Total bilirubin ^c		

^a Coagulation tests will be performed at screening only. INR will be tested in case of a suspected liver injury (see [Appendix K](#))

^b Only measured at the screening, week 14, and early termination visits (ie, visits at which patients are in a fasting state).

^c Direct and indirect bilirubin will be measured if total bilirubin is elevated.

8.5.1. Serum Chemistry, Hematology, and Urinalysis

Clinical laboratory tests (serum chemistry, hematology and coagulation, urinalysis) will be performed at the time points detailed in [Table 1](#). Patients should be fasting for at least 8 hours prior to safety laboratory assessments only at the screening, week 14, and early termination visits. Clinical laboratory tests will be performed using the central laboratory. Local laboratory testing can be used under extenuating circumstances and only following agreement with the sponsor.

Screening laboratory test abnormalities, if considered by the Investigator to be transient and inconsistent with the patient's clinical condition, may be repeated once during the screening period for confirmation. Redrawing samples if previous samples were unable to be analyzed would not count as a retest since previous result was never obtained.

